10.2.3 Treatment-Emergent Adverse Events by SOC and/or PT

Treatment-emergent adverse events will be summarized by SOC and PT; by maximum relationship to study drug as assessed by the investigator (e.g., reasonable possibility or no reasonable possibility) and SOC and PT; by maximum grade and SOC and PT; and by subject number and SOC and PT. Specific adverse events will be counted once for each subject for calculating percentages, unless stated otherwise. In addition, if the same adverse event occurs multiple times within a subject, the highest grade and level of relationship to investigational product will be reported.

In addition, treatment-emergent adverse events will be summarized by PT and sorted by decreasing frequency.

10.2.4 SAEs (Including Deaths) and Adverse Events Leading to Study Drug Discontinuation

SAEs (including deaths) and Aes leading to study drug discontinuation will be summarized by SOC and PT and in listing format.

The number of subject deaths will be summarized/listed:

- All deaths in this study regardless of the number of days after the last dose of study drug
- Deaths occurring \leq 30 days after the last dose of study drug

10.2.5 Adverse Events of Special Interest

Adverse events of special interest will be summarized by SOC and PT and will be based on standardized or company MedDRA queries (SMQs or CMQs). Adverse events of special interest along with the detailed information about the search criteria are provided in [Appendix B](#). Tabular listings of selected adverse events of special interest will be provided.

10.3 Analysis of Laboratory Data

Data collected from local laboratories, including additional laboratory testing due to an SAE, will be used in all analyses, except for Baseline where SAE-related laboratory assessments on or before the first dose of study drug will be excluded. The clinical laboratory tests defined in the protocol operations manual (e.g., hematology and clinical chemistry) will be summarized.

Baseline is defined as the last non-missing observation before the first administration of study drug if no study drug is given.

Changes from baseline will be analyzed for each chemistry, hematology parameters. The change from baseline mean, standard error, min, median, max and 95% confidence interval will be presented for the mean change from baseline for the post-baseline maximum value.

For shifts relative to National Cancer Institute Common Toxicity Criteria for Adverse Events (NCI CTCAE version 4.03), baseline and post-baseline laboratory observations will be categorized as grade 0, grade 1, grade 2, grade 3, or grade 4 according to NCI CTCAE grade version 4.03. The baseline and final grades will be defined respectively as the grade of the last measurement collected on or prior to the first dose of study drug, and as the last post-baseline measurement collected no more than 30 days after the last dose of study drug. In cases where multiple values are collected on the same day, the maximum grade value will be selected as the value for that day. If a subject had missing baseline and non-missing post-baseline for a given lab, the baseline grade will be assumed to be grade 0. The maximum NCI toxicity grade value is the value with highest NCI toxicity grade collected after the first dose of study drug.

For each lab test, cross tabulate will be generated for the number of subjects with baseline values of grade 0, grade 1, grade 2, grade 3, grade 4, or missing grade versus maximum post-baseline values of grade 0, grade 1, grade 2, grade 3, grade 4, or missing grade.

An upward shift table from grade 0 – 2 at baseline to grade 3 or 4 post-baseline (maximum) will be provided.

Treatment emergent laboratory abnormalities based on the two criteria below will be generated for each laboratory tests related to CTCAE:

1. Shifts from grade 0 (normal) at baseline to grade 1– 4 post-baseline (maximum) and worsening from an abnormal baseline value of at least one grade up post-baseline (maximum)
2. Shifts from grade 0 – 2 at baseline to grade 3 or 4 post-baseline (maximum) and from grade 3 at baseline value to grade 4 post-baseline (maximum).

For above shift tables, baseline grade of 0 (normal) will be imputed for all subjects with at least one post-baseline but missing a baseline value for each lab test.

Detailed listings of data for subjects experiencing NCI CTCAE Grade 3 to 4 blood chemistry and hematology values will be provided. All measurements collected, regardless of the number of days after the last dose of study drug, will be included in these listings.

Number and percentage of subjects meeting the Howard criteria for tumor lysis syndrome (TLS) will be presented.

The Howard Criteria for TLS is defined as two or more of the following treatment-emergent lab changes within a 24-hour period. The evaluation period for TLS is the first 7 days from the date of the first dose:

- Uric Acid > 475.8 mcmol/L,
- Potassium > 6 mmol/L,
- Inorganic Phosphorus > 1.5 mmol/L
- Calcium < 1.75 mmol/L.

TLS events are defined as:

- Clinical TLS: any event that meets Howard criteria with the following exceptions:
 - For the purpose of TLS assessment during the DLT evaluation period, only those increases in serum creatinine > 1.0 mg/dL from pre-treatment baseline will be considered clinical TLS.
 - In subjects with renal dysfunction at baseline ($\text{CrCl} < 60$ mL/min), clinical TLS is defined as the presence of laboratory TLS plus either seizures, cardiac dysrhythmia, or death.
- Laboratory TLS: any event that meets Howard criteria for laboratory TLS, that does not resolve within 72 hours despite protocol required management.

A listing of possible Hy's Law cases, defined as those who meet all of the following conditions simultaneously, will be provided: $\text{ALT} > 3 \times \text{ULN}$ or $\text{AST} > 3 \times \text{ULN}$ that is associated with an increase in bilirubin $> 2 \times \text{ULN}$ within 72 hours of each other.

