6.3 Dose-Limiting Toxicity Criteria

Tolerability in the first 6 Japanese subjects (DLT assessment period) will be determined considering all available data, including information on AEs, laboratory results, and PK data. For each of the first 6 subjects, DLTs will be assessed during the venetoclax ramp-up period for a minimum of 5 weeks and at least 1 week of venetoclax dosing at 400 mg.

A DLT is defined as any Grade ≥ 3 AE considered to be at least possibly related to study drug (ibrutinib and/or venetoclax) and occurring during the DLT assessment period with the following clarifications:

Non-Hematologic DLTs:

- Grade ≥ 3 nausea, vomiting, or diarrhea, uncontrolled despite maximum medical supportive care and persisting > 5 days
- Grade 3 fatigue persisting > 7 days
- Grade 3 infection is not a DLT; however, an infection with life-threatening consequences or requiring urgent intervention (Grade 4) will be considered a DLT
- Treatment delay of any study drug of > 7 consecutive days for toxicity.

Hematologic DLTs:

- Grade 3 neutropenia is not a DLT; however, Grade 4 neutropenia ($ANC < 500/\text{mm}^3$) lasting for > 7 days is a DLT
- Grade 3 or 4 neutropenia complicated by fever $\geq 38.5^\circ\text{C}$ or infection
- Grade 4 thrombocytopenia ($< 25,000/\text{mm}^3$) that persists for > 7 days
- Grade 3 or 4 thrombocytopenia associated with Grade 2 or greater bleeding
- Grade 3 anemia is not a DLT; however, Grade 4 anemia is a DLT
- Treatment delay of any study drug > 7 consecutive days for hematologic toxicity.

In addition, clinically important or persistent toxicities that are not included in the above criteria will be considered a DLT following review by the Sponsor and the investigators.

Subjects who miss $\geq 20\%$ of the planned doses of venetoclax or ibrutinib for reasons other than toxicity (e.g., non-compliance, withdrawal of consent, disease progression) during the DLT assessment period, or subjects who do not complete the DLT assessment period for any reason other than a DLT will be considered non-evaluable and will need to be replaced.

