7.4 Statistical Analyses for Safety

The safety and tolerability of venetoclax in combination with ibrutinib will be assessed by evaluation of study drug exposure, DLTs, AEs, SAEs, and deaths, as well as changes in laboratory parameters, physical examinations, electrocardiogram (ECG), and vital sign measurements.

Tolerability of venetoclax and ibrutinib combination will be assessed for the first 6 evaluable subjects, where an evaluable subject is defined as a subject who has received the combination for a minimum of 5 weeks and at least 1 week of venetoclax dosed at 400 mg.

Details on the statistical analyses for safety are provided in the SAP.

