Appendix B. Definition of Adverse Events of Special Interest

Adverse Events of Special Interest (AESI) and Selected AEs will be identified using the following search criteria:

Risk	Search Criteria
Tumor Lysis Syndrome	SMQ 20000219 – "Tumour lysis syndrome" (Narrow-scope)
Neutropenia – expanded search	Neutropenia CMQ 80000171
Neutropenia	PT terms – "Neutropenia" and "Neutrophil count decreased"
Serious Infection	SAEs in the SOC of "Infections and Infestations"
Second Primary Malignancy	SMQ 20000194 – "Malignant tumours" (Narrow) and SMQ 20000217 - "Myelodysplastic syndromes" (Narrow)
Lymphopenia	PT terms – "Lymphopenia" and "Lymphocyte count decreased"
Anemia	PT terms – "Anaemia" and "Haemoglobin decreased"
Thrombocytopenia	PT terms – "Thrombocytopenia" and "Platelet count decreased"
Major Hemorrhage	SMQ – "Haemorrhagic disorders" (narrow)
Cardiac arrhythmia	
1. Atrial fibrillation: PT= Atrial fibrillation2. Cardiac arrhythmias: Cardiac arrhythmias SMQ broad (excluding PT of Atrial fibrillation)3. Ventricular tachyarrhythmias (as a sub-analysis under Cardiac arrhythmias recognizing there is overlap): Ventricular tachyarrhythmias SMQ narrow

Appendix C. Potentially Clinically Important Criteria for Safety**Table C-1. Criteria for Potentially Clinically Important Vital Sign Values**

Vital Signs Variables	Criterion	Definition of Potentially Clinically Significant
Systolic blood pressure	High	Value \geq 160 mmHg
Diastolic blood pressure	High	Value \geq 100 mmHg
Heart rate (bpm)	Low	Value < 50 bpm
	High	Value \geq 120 bpm
Temperature	Low	Value < 36°C
	High	Value \geq 38.0°C

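### The only numeric laboratory change summary uses the post-baseline maximum for every parameter, so where low values are harmful it omits the nadir, understates falls and can show small or transient ones as rises.

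*SAP*

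**What the plan says.** The rule is in SAP 10.3 (Analysis of Laboratory Data). Its scope is general: "Changes from baseline will be analyzed for each chemistry, hematology parameters". The statistics listed are mean, standard error, min, median, max and a 95% confidence interval, and they "will be presented for the mean change from baseline for the post-baseline maximum value". Parameters are not divided by direction of harm.

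The protocol offers no alternative. Section 7.4 closes with "Details on the statistical analyses for safety are provided in the SAP".

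The same SAP section has a separate set of analyses based on toxicity grade, with its own definition of the worst value: "The maximum NCI toxicity grade value is the value with highest NCI toxicity grade collected after the first dose of study drug". These include "An upward shift table from grade 0 – 2 at baseline to grade 3 or 4 post-baseline (maximum) will be provided", two definitions of treatment-emergent laboratory abnormality, and, for individual subjects, "Detailed listings of data for subjects experiencing NCI CTCAE Grade 3 to 4 blood chemistry and hematology values will be provided".

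**The concern.** A single maximum rule suits parameters such as creatinine or ALT, where harm is upward. It does not suit blood counts. The documents treat low counts as a central expected toxicity. Protocol 6.3 builds dose-limiting toxicity criteria on them (for example "Grade 3 neutropenia is not a DLT; however, Grade 4 neutropenia", with a duration attached). Protocol 6.2 has modification rules for haematologic toxicity. SAP Appendix B searches for neutropenia, lymphopenia, anaemia and thrombocytopenia. Low calcium is one of the tumour lysis criteria in SAP 10.3.

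For these parameters the table would report a mean and confidence interval at the visit least affected by treatment. At stake is whether the one continuous laboratory summary describes the toxicity of interest, or appears to contradict the grade tables beside it in the report.

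**Working it through.** The plan gives no figure to reproduce on this point. The check is a reading of the text, a result that needs no model, and a simulation for scale.

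**Reading.** Two words could be taken to rescue the table.
- The listed min is one of the statistics describing the distribution of changes across subjects. It is the smallest change to the maximum, not a change to the lowest value.
- The maximum in this sentence is a maximum value. The highest-grade definition later in the section is a separate definition for the grade analyses, and the change-from-baseline sentence does not refer to grade.

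**Without a model.** Let B be a subject's baseline and X1, ..., XK the post-baseline values.
- Planned: Dmax = max(X1, ..., XK) - B.
- At the nadir: Dmin = min(X1, ..., XK) - B.
- Dmax - Dmin = max(X) - min(X), which is at least 0. The planned change never shows a deeper fall than the nadir, and shows a shallower one whenever the post-baseline values differ.
- Dmax is negative only if every post-baseline value is below baseline. One value above baseline makes that subject's change positive, however deep the nadir was.

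The second condition is easily met here. Protocol 6.2, Table 2 provides for interrupting venetoclax for specified haematologic toxicity, with resumption after recovery and G-CSF where indicated. Protocol 5.4 permits neutrophil growth factors and transfusion. The maximum may then be a recovered or supported value.

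**Simulation for scale.** The following inputs are assumptions, not document figures: independent normal values, within-subject SD of 1, K = 8, 12 or 20 post-baseline samples, and 200,000 simulated subjects per setting. For a sustained fall of d, theory gives mean Dmax = e(K) - d and mean Dmin = -e(K) - d, where e(K) is the expected maximum of K standard normal values. The no-change row gives e(K) = 1.42, 1.63 and 1.87.

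| Pattern (SD units) | Mean change at maximum, K = 8 / 12 / 20 | Mean change at minimum, K = 8 / 12 / 20 |
|---|---|---|
| No true change | +1.42 / +1.63 / +1.87 | -1.42 / -1.63 / -1.87 |
| Sustained fall of 1 | +0.42 / +0.63 / +0.87 | -2.43 / -2.62 / -2.87 |
| Sustained fall of 2 | -0.57 / -0.37 / -0.13 | -3.42 / -3.63 / -3.87 |
| Sustained fall of 3 | -1.58 / -1.37 / -1.14 | -4.43 / -4.63 / -4.87 |
| Fall of 3 in half the samples, then recovery | +1.03 / +1.27 / +1.54 | -4.03 / -4.26 / -4.54 |

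Three results follow.
- Setting e(K) - d = 0, a sustained fall appears as a mean rise only when it is smaller than 1.42 SD (K = 8) to 1.87 SD (K = 20).
- With recovery, the maximum hardly responds to depth. At K = 8, transient falls of 2, 3 and 5 SD give +1.04, +1.03 and +1.03 at the maximum, against -3.04, -4.03 and -6.03 at the minimum.
- The no-change row is symmetric, so the minimum carries the same drift with the opposite sign. That row shows how extremes behave. It does not measure what is wrong with the current rule.

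**The case against.** The strongest reply is that nothing of clinical consequence depends on this table. For counts graded on low values, the highest toxicity grade is the grade at the nadir, so the shift tables and both treatment-emergent abnormality criteria already capture it. Grade 3 to 4 haematology values are listed by subject, and cytopenias are also found through the preferred-term searches in SAP Appendix B. Dose-limiting toxicity and dose-modification decisions rest on individual subjects' grades and counts, not on a mean change. Everything other than the primary endpoint is descriptive (Protocol 7.6, SAP 13.0), in about 12 subjects. All of this stands, and it limits the point to one table.

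It also rules out two stronger readings. A reader might infer that falls in blood counts will necessarily be reported as rises, with a confidence interval in the wrong direction. The rule does not imply that: if every post-baseline value lies below baseline the change stays negative, and under the assumptions above sustained falls of 2 to 3 SD remain mean falls. A reader might also infer that cytopenia would go undetected. The outputs just listed show otherwise.

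The reply does not make the table sound. A numeric summary with a confidence interval, taken at the least harmful value, remains uninformative about falls whatever the other tables show. If the sponsor intended the worst value in each direction, the sentence does not say so and still needs correcting.

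**Conclusion.** The point holds in limited form. As written, the single continuous laboratory change table takes the least harmful value for neutrophils, platelets, haemoglobin and calcium, and for albumin if measured (Protocol 6.2 lists it only if available). It omits the nadir, understates falls, and can reverse the sign of small or transient ones.

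The direction of the understatement needs no assumption. The SD figures are illustrative only: they rest on independent normal values and assumed sample counts, and the same drift applies with opposite sign to the minimum. How often the sign would reverse in this trial cannot be determined from the documents.

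The primary analysis, tolerability decisions and detection of cytopenia are not affected. This is a minor but clear defect in one descriptive output, and it is worth correcting because the correction is cheap.

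**What to change.** Replace the single rule in SAP 10.3 with one set by direction of harm:
- **Post-baseline minimum:** neutrophils, platelets, haemoglobin, calcium, and albumin if measured.
- **Post-baseline maximum:** creatinine, ALT, AST, bilirubin, uric acid and phosphorus.
- **Both:** potassium, and lymphocytes and white cells. For the last two, SAP Appendix B looks for lymphopenia while Protocol 6.2 treats a very high white cell count as a leukostasis risk.
- **Default:** both, for any parameter not assigned above. The full test list is in the Operations Manual, so a default is needed.

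A table footnote should say that extreme values drift away from baseline as the number of samples grows, in either direction.

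The cost is one or two SAP sentences and a small programming change, with no new data. Protocol Appendix J states that the primary analysis is complete, so the change cannot now be presented as pre-specified for that analysis. Apply it to the remaining reporting, or issue it as a supplementary table labelled as added afterwards. Because the output is descriptive, no error-rate adjustment is needed.

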10.4 Analysis of Vital Signs

Vital sign variables will be evaluated based on potentially clinically important (PCI) criteria ([Appendix C](#), Table C-1). For each vital sign PCI criterion, the number and percentage of subjects who have a vital sign value meeting the criteria will be summarized. Listings will be provided to summarize subject-level vital sign data for subjects meeting PCI criteria.

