The ongoing SYMPATICO Study (ibrutinib and venetoclax in R/R MCL), which is the basis of Study M20-075, is evaluating the combination of ibrutinib at 560 mg and venetoclax at a target dose of 400 mg in subjects with R/R MCL. The study started with an open-label safety run-in period to evaluate the occurrence of TLS and dose-limiting toxicities (DLTs) with the concurrent administration of ibrutinib and venetoclax. The safety run-in period of the study included 21 patients with R/R MCL, 15 patients at high-risk for TLS, and 6 patients at low risk for TLS. One laboratory TLS event occurred in a patient at high-risk for TLS. No clinical TLS events occurred. No TLS event occurred in patients at low risk for TLS. Dose-limiting toxicities were observed in 3 patients at high-risk for TLS; Grade 4 neutropenia (n = 1), Grade 4 infection (n = 1), and Grade 3 atrial fibrillation plus grade 3 hypotension (n = 1). No DLT event occurred in patients at low risk for TLS. As pre-specified in the protocol, the combination dosing schedule of ibrutinib 560 mg + venetoclax 400 mg was recommended for both subjects at high and low risk for TLS, and the randomization part of the study is ongoing with the same schedule as the safety run-in period. The CR rate was 48% in all patients, 67% in patients at low risk for TLS, and 40% in patients at high-risk for TLS, with a longer follow-up time for patients at low risk for TLS than high-risk for TLS (median follow-up, 14 versus 8 months).²⁶

Study M20-075 will evaluate the safety and efficacy of the combination of venetoclax at a target dose of 400 mg and ibrutinib at 560 mg in Japanese subjects with R/R MCL.

Clinical Hypothesis

The combination of venetoclax and ibrutinib can be safely administered and will result in high CRs in Japanese subjects that is similar to that observed in non-Japanese subjects.

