- Within the first 24 hours after either the first dose or dose escalation, if any laboratory criteria below are met, the patient should be hospitalized for monitoring and the investigator notified. No additional venetoclax doses should be administered until resolution. A rapidly rising serum potassium is a medical emergency.
- Nephrology (or other acute dialysis service) should be contacted/consulted (per institutional standards to ensure emergency dialysis is available) on admission for any subject hospitalized prophylactically or in response to laboratory changes.
- IV fluids (e.g., D5 1/2 normal saline) should be initiated at a rate of at least 1 mL/kg/hr rounded to the nearest 10 mL (target 150 to 200 mL/hr; not < 50 mL/hr). Modification of fluid rate should also be considered for individuals with specific medical needs.
- Monitor for symptoms or signs of tumor lysis syndrome (TLS) (e.g., fever, chills, tachycardia, nausea, vomiting, diarrhea, diaphoresis, hypotension, muscle aches, weakness, paresthesias, mental status changes, confusion, seizures). If any clinical features are observed, recheck potassium, phosphorus, uric acid, calcium and creatinine within 1 hour STAT.
- Vital signs should be taken at time of all blood draws or any intervention.
- The management recommendations below focus on the minimum initial responses required. If a diagnosis of TLS is established, ongoing intensive monitoring and multi-disciplinary management will be per institutional protocols.

In addition to the recommendations in the table below:

- For potassium increase ≥ 0.5 mmol/L from baseline, or any value > 5.0 mmol/L, recheck potassium, phosphorus, uric acid, calcium and creatinine within 1 hour STAT and follow first guideline.
- For phosphorus increase of > 0.5 mg/dL AND > 4.5 mg/dL, administer phosphate binder and recheck potassium, phosphorus, uric acid, calcium and creatinine within 1 hour STAT.

Abnormality	Management Recommendations ^{1,2}
Hyperkalemia (including rapidly rising potassium)	

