3.4 Safety Endpoints

Safety and tolerability will be assessed by evaluating DLTs, adverse events, physical examinations, and changes in laboratory data (hematology, chemistry, and urinalysis) and vital signs for the entire study treatment duration.

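### The SAP's only vital-sign analysis sets no lower limit for blood pressure, so low readings not reported as adverse events are counted in no planned summary (minor)

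*SAP*

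**What the plan says.** SAP 3.4 (and Protocol 3.4) defines the safety assessment to include "changes in laboratory data (hematology, chemistry, and urinalysis) and vital signs for the entire study treatment duration". Protocol 7.4 likewise includes changes in vital sign measurements.

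The analysis meant to deliver this is SAP 10.4: "Vital sign variables will be evaluated based on potentially clinically important (PCI) criteria". It counts the subjects meeting each criterion, gives percentages, and adds a listing: "Listings will be provided to summarize subject-level vital sign data for subjects meeting PCI criteria".

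The criteria are in SAP Appendix C, Table C-1, titled "Criteria for Potentially Clinically Important Vital Sign Values". The table has six rows:

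- Systolic pressure: high only, at or above 160 mmHg.
- Diastolic pressure: high only, at or above 100 mmHg.
- Heart rate: low, below 50 bpm; high, at or above 120 bpm.
- Temperature: low, below 36°C; high, at or above 38.0°C.

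The protocol mentions low blood pressure in three places. Section 2.1 reports that one of the three patients with DLTs in the SYMPATICO safety run-in (21 patients) had "Grade 3 atrial fibrillation plus grade 3 hypotension". Appendix H lists it among the symptoms or signs of TLS to monitor: "diaphoresis, hypotension, muscle aches, weakness". Appendix G includes it in the clinical TLS column, where it is attributed to hypocalcemia.

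**The concern.** A table of this kind catches out-of-range values objectively, whether or not anyone reports an event. Here it does so in both directions for heart rate and temperature but in one direction only for blood pressure. The missing direction is one that the protocol itself mentions as a safety sign for this combination.

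At stake is the completeness of the descriptive safety output. A series of low readings that no investigator reports as an AE would leave no trace in any planned count. The plan would also not fully deliver its own endpoint, which refers to changes in vital signs: a count of threshold crossings, one-sided for blood pressure, is not a summary of change.

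**Working it through.** The plan gives no figure to reproduce on this point. The check is to apply the rule as written and then look for another analysis that would pick up what it leaves out.

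**Step 1: the rule.** With S and D for systolic and diastolic pressure in mmHg, H for heart rate in bpm and T for temperature in °C, Table C-1 flags a reading if S ≥ 160, or D ≥ 100, or H < 50, or H ≥ 120, or T < 36, or T ≥ 38.0. If S < 160 and D < 100, neither pressure condition is met, however low the pressure.

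**Step 2: test readings.** These are invented to exercise the rule; they are not trial data.

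| S/D | H | T | Flags raised |
|---|---|---|---|
| 70/40 | 100 | 36.8 | none |
| 85/50 | 119 | 37.5 | none |
| 70/40 | 125 | 36.8 | heart rate high only |
| 70/40 | 100 | 38.2 | temperature high only |
| 165/90 | 80 | 36.8 | systolic high |

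Every whole-number combination of S from 0 to 159 and D from 0 to 99, with H = 80 and T = 36.8, was also tried. None raised a flag. Rows three and four show the one incidental route: the subject enters the listing for another reason, and the low pressure may be visible there, but it is not counted as low.

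**Step 3: other analyses.**

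- SAP 10.3 plans change from baseline for chemistry and hematology parameters only. There is no mean, minimum, shift or change summary for blood pressure.
- The searches in SAP Appendix B name arrhythmia, hemorrhage, cytopenias, infection, second malignancy and TLS. None is set up for hypotension.
- SAP 10.2 tabulates AEs by system organ class, preferred term and maximum grade, with overview rows for Grade 3, Grade 4 and DLT events. Hypotension recorded as an AE appears here.
- Protocol 6.1 decides which readings reach those tables. A vital-sign change is an AE only if it leads to discontinuation from the study, needs therapeutic intervention, meets protocol-specific criteria, or is judged an AE by the investigator.

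**Step 4: result.** The uncounted set is exactly the low blood pressure readings that meet none of the conditions in Protocol 6.1. The documents give no basis for estimating how many there would be.

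**Step 5: extraction.** The low rows for heart rate and temperature survived in the text, and nothing in the table marks a redaction. The missing rows do not look like a product of the PDF reading.

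**The case against.** The strongest reply is that hypotension of clinical consequence is already covered. An episode that needs treatment is an AE under Protocol 6.1. A Grade 3 or higher AE at least possibly related to study drug in the assessment period is a DLT under Protocol 6.3, subject to clarifications that do not mention hypotension. The parent-study case was itself reported as a DLT, and atrial fibrillation, which occurred with it, has its own search in SAP Appendix B. This stands, and it confines the gap to readings not reported as AEs.

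The TLS link is also limited. TLS has its own analyses: the Howard laboratory criteria in SAP 10.3 and a search in Appendix B. In Protocol Appendix G, hypotension counts only when attributed to hypocalcemia, which a pressure cut-off cannot establish, and Appendix H is bedside guidance. This stands too. The TLS passages show that the protocol regards the sign as relevant; they do not show that TLS would be missed.

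Three stronger readings are tempting, and the documents support none of them.

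- A reader might infer that the table will report no hypotension whatever happens. It has no hypotension row, so it is silent and makes no false statement.
- A reader might project the one run-in case onto 12 subjects and call the result the chance of a missed event. Protocol 2.1 reports DLTs only, not every case of hypotension, and a Grade 3 event is the kind that the AE and DLT tables would catch.
- A reader might infer from the absence of a time window in SAP 10.4 that screening readings count. SAP 3.4 ties the assessment to the treatment period, which largely answers this; a clarifying sentence is enough.

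**Conclusion.** The point holds as a minor one. Low blood pressure readings that do not become AEs are counted in no planned summary, while the same table counts low values of heart rate and temperature. The planned analysis also falls short of the stated endpoint, because no change in vital signs is summarized.

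The consequence is confined to descriptive safety output in a single-arm study of about 12 subjects. The primary endpoint, the DLT rule, AE reporting and type I error are unaffected. Protocol Appendix J says that the primary analysis is complete, so a change would reach later safety outputs only.

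The conclusion assumes that Table C-1 is complete as printed and that no vital-sign output is specified outside the two documents.

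**What to change.** 1. Add low rows for systolic and diastolic pressure to SAP Appendix C, Table C-1. The sponsor prespecifies the limits. They are flags for analysis and imply no clinical action.
2. Add a sentence to SAP 10.4 saying that only readings taken on treatment, after the first dose of study drug, count towards the criteria, in line with SAP 3.4.
3. Preferably, add a change-from-baseline summary of vital signs, so that the analysis matches the endpoint in SAP 3.4 and Protocol 7.4.

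The cost is two table rows, one sentence and, if the third item is taken up, one further descriptive table. No new data are needed, and no multiplicity question arises because these analyses are descriptive under SAP 13.0. The only downside is a few more rows of output.
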